9.2.3.4 Ophthalmologic Examination

The OE results during Part 1 TE period will be presented in individual subject data listings.

9.2.3.5 Physical Examination

Abnormal PE findings will be presented as an individual subject data listing only as appropriate.

9.3 Final Analyses

The final analysis will be conducted after all subjects have completed the study or have prematurely discontinued.

9.3.1 Background Characteristics

9.3.1.1 Subject Disposition

A disposition table will be provided for the study Part 2 with the number of subjects in:

- FAS, Part 2 (dosed during the study Part 2)
- Safety Set, Part 2 (dosed during the study Part 2)

The number and percentage (based on the FAS, Part 2) of subjects in each of the following disposition categories will be summarized for the study Part 2 by treatment sequence from Part 1 to Part 2:

- Completed Part 2 treatment
- Completed study
- Prematurely discontinued treatment during Part 2 and the reason for discontinuation

- Prematurely discontinued study participation during Part 2 and the reason for discontinuation

A listing will be provided for subjects who discontinued treatment or who discontinued study with reasons for discontinuation during Part 2.

9.3.1.2 Study Drug Exposure

Duration of study drug exposure on LUM/IVA during the study Part 2 is defined as last LUM/IVA dose date of Part 2 – first LUM/IVA dose date of Part 2 + 1 day, regardless of any interruptions in dosing.

Duration of study drug exposure on LUM/IVA during the Part 2 Safety Period (in weeks) will be summarized descriptively based on the Safety Set, Part 2 for overall LUM/IVA treatment group by the number of subjects (n), mean, SD, median, min, and max. It will also be summarized as a categorical variable by intervals using counts and percentages.

9.3.1.3 Study Drug Compliance

Percentage of study drug compliance during the study Part 2 will be summarized descriptively based on the FAS, Part 2 and presented by overall LUM/IVA treatment group.

[figure not shown]
Study drug compliance will be calculated as: $100 \times (1 - [\text{total number of days of LUM/IVA interrupted prior to the date of last dose of LUM/IVA in Part 2}] / [\text{duration of LUM/IVA exposure in Part 2}])$. A study drug interruption on a given day is defined as an interruption of any study drug on that day. A study drug interruption that continues through the end of the study participation (i.e., subject does not resume study drug before the end of the study participation) will not be included in the compliance calculation.

[figure not shown]
Descriptive summary statistics include the number of subjects (n), mean, SD, median, min, and max. It will also be summarized in categories: <80% and ≥80% using frequency tables. A listing containing subjects with study drug interruptions will be provided.

In addition, percentage of stick packs/tablets taken will be calculated using the following formula: $100 \times [(\text{total number of stick packs/tablets dispensed during Part 2}) - (\text{total number of stick packs/tablets returned during Part 2})] / (\text{total number of stick packs/tablets planned to be taken per day during Part 2} \times \text{duration of Part 2 drug exposure in days})$. Summary similar to those for the study drug compliance will be produced based on the FAS, Part 2.

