**Table 3-2 Study VX16-809-121: Treatment Period and Safety Follow-up Visit**

Event/Assessment a	Treatment Period									ETT Visit b	Safety Follow-up Visit c
	Part 1: Placebo-controlled Period				Part 1/ Part 2 d	Part 2: Open-label Period e					
	Day 1	Day 3 (± 1 Day)	Day 15 (± 3 Days)	Weeks 12, 24, 36 (± 7 Days)	Week 48 (± 7 Days)	Day 338 f (± 1 Day)	Day 350 (± 3 Days)	Weeks 60, 72, 84 (± 7 Days)	Week 96 (± 7 Days)		
Clinic visit	X		X	X	X		X	X	X	X	X
Telephone contact g		X				X					
Randomization h	X										
Stature and weight i	X		X	X	X		X	X	X	X	X
Vital signs j	X k		X	X	X k		X	X	X	X	X
OE l					X m				X m,n	X m,n	X m,n
Full PE o	X			Week 24	X			Week 72	X	X	X

- a Assessments will be performed before study drug dosing unless noted otherwise (Section 11.1).
- b If the ETT Visit occurs 10 days or later after the last dose of study drug, the Safety Follow-up Visit will not be required. Subjects who prematurely discontinue study drug treatment for AEs should be followed until the AE is considered resolved.
- c The Safety Follow-up Visit is required for 1) subjects who complete their ETT Visit <10 days after the last dose of study drug and 2) subjects who interrupt study drug treatment and complete their Week 96 Visit <10 days after the last dose of study drug; it is not required for subjects who continue onto commercially available, physician-prescribed LUM/IVA within 2 weeks (± 4 days) of completing study drug treatment at the Week 96 or ETT Visit.
- d The first open-label dose of LUM/IVA will be the dose administered at the Week 48 Visit after completion of the predose assessments.
- e If the subject's Week 48 Visit is delayed, all subsequent visits must be delayed accordingly based on the actual Week 48 Visit date.
- f The Day 338 Visit (telephone contact) should occur 1 to 3 days after the actual date of the Week 48 Visit, regardless of whether it is Study Day 338.
- g Telephone contacts will be made to assess the subject's status, any AEs, medications, treatments, and procedures.
- h Randomization must only occur after all inclusion and exclusion criteria are met and before the first dose of study drug. Randomization will be done through IWRS and may occur on Day -1.

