**Table 9-2 Study Drug Administration**

Treatment Arm	Time	LUM/IVA (Number of Stick Packs/Tablets)	Placebo (Number of Stick Packs)
LUM/IVA (Part 1)			
Subject screening weight <14 kga LUM 100 mg/IVA 125 mg q12h	AM	1 stick pack	None
	PM	1 stick pack	None
Subject screening weight ≥14 kga LUM 150 mg/IVA 188 mg q12h	AM	1 stick pack	None
	PM	1 stick pack	None
Placebo (Part 1 Only)			
LUM/IVA matching placebo	AM	None	1 stick pack
	PM	None	1 stick pack
LUM/IVA (Part 2)			
Subject <6 years of age and screening weight <14 kga LUM 100 mg/IVA 125 mg q12h	AM	1 stick pack	NA
	PM	1 stick pack	NA
Subject <6 years of age and screening weight ≥14 kga LUM 150 mg/IVA 188 mg q12h	AM	1 stick pack	NA
	PM	1 stick pack	NA
Subjects ≥6 years of ageb LUM 200 mg/IVA 250 mg q12h	AM	2 tablets	NA
	PM	2 tablets	NA

IVA: ivacaftor; LUM: lumacaftor; NA: not applicable; q12h: every 12 hours

a Doses are based on the subject's weight at screening. No downward dose adjustments will be made if a subject's weight decreases. If a subject subsequently weighs ≥14 kg at 2 consecutive visits, the dose will be adjusted to LUM 150 mg/IVA 188 mg q12h at the second visit where weight ≥14 kg.

b Subjects who turn 6 years of age at or after the Week 48 Visit will receive LUM 200 mg/IVA 250 mg q12h (starting at the Week 48 Visit or the next scheduled visit after turning 6 years of age), regardless of weight.

Study drug will be administered within 30 minutes from the start of consuming fat-containing food such as a standard "CF" high-fat, high-calorie meal or snack according to the following guidelines:

1. All doses of study drug (morning and evening, as applicable) should be administered at approximately every 12 hours ( $\pm$  2 hours) on each dosing occasion (e.g., if the morning dose is administered at 08:00 on Day 1, all subsequent morning doses should be administered between 06:00 and 10:00).
2. The granule formulation will be dispensed by opening the stick packs containing the granules and mixing the granules with the approved foods and liquids listed in the study manual (e.g., apple sauce). Each dose will be comprised of the approved food or liquids into which the granules from the stick packs are mixed. Details on preparing study drug will be provided in the pharmacy manual.

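### The Part 2 percentage of stick packs and tablets taken uses one planned daily count, so it is wrong for a child who changes from granules to tablets after Week 48

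*SAP*

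**What the plan says.** SAP 9.3.1.3 gives two compliance measures for Part 2. The main one is based on days of interruption. The second, added to it, is a unit count.

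- **Numerator of the unit count:** the "total number of stick packs/tablets dispensed during Part 2" minus those returned, with stick packs and tablets pooled.
- **Denominator:** the "total number of stick packs/tablets planned to be taken per day during Part 2" multiplied by the "duration of Part 2 drug exposure in days". SAP 9.3.1.2 defines that duration as "last LUM/IVA dose date of Part 2 – first LUM/IVA dose date of Part 2 + 1 day", with no split by formulation.
- **Presentation:** "Summary similar to those for the study drug compliance will be produced based on the FAS, Part 2". The summary referred to includes the <80% and ≥80% categories.

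Protocol Table 9-2 sets 1 stick pack morning and evening for children under 6 in either weight band, and 2 tablets morning and evening from age 6. Its footnote b says "Subjects who turn 6 years of age at or after the Week 48 Visit will receive LUM 200 mg/IVA 250 mg q12h". By the same footnote, the change takes effect at Week 48 itself or, for a later birthday, at whichever planned visit follows it.

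**The concern.** The planned number of units per day doubles, from 2 to 4, on the day a child moves from granules to tablets. When that day falls inside Part 2, the formula asks for one daily count where two apply in turn, and the visible SAP text has no rule for the change.

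The formula looks carried over from Part 1 (SAP 9.2.1.6). There it works, because every child is planned 2 stick packs a day throughout. The Part 2 version adds tablets but keeps the single count.

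At stake is the unit-count table. Some fully adherent children could be listed as under 80% compliant, or shown as taking far more than planned. Two programmers following the same text could report different figures for the same child.

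**Working it through.** The plan states no numerical result for this measure, so there is no figure to reproduce. The formula is applied to a child who takes every planned dose and returns the rest.

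**Inputs**
- Units per day: 1 + 1 = 2 on granules, 2 + 2 = 4 on tablets (Protocol Table 9-2).
- Part 2 exposure D: 48 × 7 = 336 days.
- Granule days in Part 2 before the change, t: 14 for the Day 350 visit (Part 2 Day 15 in SAP Appendix A), 84 for Week 60, 168 for Week 72, 252 for Week 84.
- Single daily count k: 2 or 4.

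**Formulas**
- Units taken: U = 2t + 4(D − t).
- Reported percentage: P = 100 × U / (k × D).

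**Check where the count is constant.** Granules throughout: 672 / (2 × 336) = 100%. Tablets from Week 48: 1344 / (4 × 336) = 100%. The formula is right for both.

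**Change after Week 48, full adherence, D = 336**

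| Change at | t | U | k = 4: U / 1344 | k = 2: U / 672 |
|---|---|---|---|---|
| Day 350 | 14 | 1316 | 97.9% | 195.8% |
| Week 60 | 84 | 1176 | 87.5% | 175.0% |
| Week 72 | 168 | 1008 | 75.0% | 150.0% |
| Week 84 | 252 | 840 | 62.5% | 125.0% |

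The true value is 100% in every row.

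**When k = 4 falls below 80%.** P = 100 × (1 − t/(2D)), which is under 80 when t > 0.4D = 134.4 days. At full exposure that means Week 72 and Week 84 only. A child who changes at Week 60 would fall below 80% only if exposure were shorter than 84 / 0.4 = 210 days.

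**What k = 2 can hide.** If adherence is even over time, the true adherence reported as 80% is 80 / (P/100): 40.9% (Day 350), 45.7% (Week 60), 53.3% (Week 72) and 64.0% (Week 84).

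**Sensitivity to D, k = 4.** At D = 337 (the SAP's + 1 day), Weeks 72 and 84 give 75.1% and 62.6%. At D = 396 (a 60-day extension for the Week 96 MRI), they give 78.8% and 68.2%. The category does not change.

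**How many children.** The documents give no age distribution. Assume ages at consent uniform over 2 to under 6 years (1461 days) and all 50 children entering Part 2.
- Change at Day 350 to Week 84 (sixth birthday in the 252 days after Week 48): 252 / 1461 = 17.2%, or 8.6 children.
- Change at Week 72 or 84 (birthday in the 168 days after Week 60): 168 / 1461 = 11.5%, or 5.7 children.
- With the 10% dropout assumed in Protocol 12.1, 45 children: 7.8 and 5.2.

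**The case against.** The strongest reply is that the denominator is unclear rather than wrong. Planned units per day could be read as a quantity that varies by day and is accumulated over exposure, which gives 100%. The authors wrote tablets into the Part 2 formula, so they had the change of formulation in mind. A sensible programmer might well do this. But the text multiplies one number per day by one total duration, so the accumulating reading departs from what is written. Part of the derived-variable list in SAP Appendix A is blacked out, so one can say only that the visible text has no rule. The formula itself is intact.

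The reply is right about reach. A reader might infer more than the documents support:

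- **That every child who changes is put under 80%.** This needs k = 4 and, at full exposure, a change at Week 72 or 84. With k = 2 no fully adherent child falls below 80%.
- **That all children turning 6 in Part 2 are affected**, 336 / 1461 = 23% on the same age assumption. A child who turns 6 after the Week 84 visit next attends at Week 96, the last dose, and has essentially no tablet period.
- **That separate percentages for packs and tablets over the full duration would show 50%.** The formula pools the two, so this case does not arise from it.
- **That Part 2 compliance as a whole is spoiled.** The interruption-based measure uses no unit counts. The protocol's own measure (12.3.2.4) counts dosing occasions, which stay at two a day.
- **That protocol deviations are miscounted.** SAP 9.2.1.7 lists under 80% compliance as a potential important deviation but names no measure, and a team reviews each case. The error would reach that list only if the unit count were used.

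**Conclusion.** The formula is wrong as written for a child who changes formulation at Day 350 or at Week 60, 72 or 84: neither daily count returns 100% at full adherence. Children who stay on granules, or who start tablets at the Week 48 Visit, are unaffected when their own planned count is used.

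The direction of the error depends on the count chosen. One choice understates adherence enough to misclassify later changers; the other overstates it and can conceal non-compliance. The number of children rests on the assumed age distribution and on entry to Part 2, so it indicates scale only.

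The point is minor. It concerns a secondary descriptive summary of the open-label period. The efficacy analyses and the main compliance measure are not touched.

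**What to change.** In SAP 9.3.1.3, define the denominator as planned units summed over formulation periods: 2 × days on granules + 4 × days on tablets, taking the daily counts from Protocol Table 9-2 as it stands. The two sets of days should add up to the Part 2 exposure duration, and units dispensed minus returned should be summed over the same periods. At D = 336 the planned units become 1316, 1176, 1008 and 840 for the four change visits, equal to the units taken, so each fully adherent child scores 100%.

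It would also help to state in SAP 9.2.1.7 which compliance measure the 80% deviation rule uses.

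The cost is a sentence or two of SAP text. Protocol 10.4 already requires dates and amounts dispensed and returned to be kept, so no new data collection appears to be needed. SAP section 3 allows amendment before the database lock for the final analysis. Dosing is not changed.

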9.3.1.4 Important Protocol Deviations

IPDs (from the clinical database or from the site deviation log) during Part 2 will be summarized descriptively based on the FAS, Part 2 and presented by treatment sequence from Part 1 to Part 2. Additionally, IPDs will be provided in an individual subject data listing.

9.3.3 Safety Analysis

Safety analyses specified for the Part 1 analysis (Section 9.2.3) will be performed similarly for the Part 2 Safety Period based on the Safety Set, Part 2 in FA.

Unless otherwise specified, analyses of adverse events and threshold analysis for clinical laboratory and vital signs will be summarized for the Part 2 Safety Period and presented for overall LUM/IVA treatment group. Analyses on change from LUM/IVA baseline of clinical laboratory and vital signs will be summarized at each Part 2 visit and presented by treatment sequence from Part 1 to Part 2.

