#### 12.3.4.1 Adverse Events

AEs will be classified as pretreatment AEs or TEAEs, defined as follows:

**Pretreatment AE:** any AE that started before the first dose date of study drug

**TEAE:** any AE that worsened (either in severity or seriousness) or that was newly developed at or after the first dose date of study drug through the end of the TE Period

For AEs with completely missing or partially missing start dates, if there is no clear evidence that the AEs started before or after study treatment, the AEs will be classified as TEAEs.

Details for imputing missing or partial start dates of AEs are described in the SAP.

AE summary tables will be presented for TEAEs only, overall and by treatment group, and will include the following:

- All TEAEs
- TEAEs by strongest relationship
- TEAEs by maximum severity
- TEAEs leading to treatment discontinuation
- Serious TEAEs
- TEAEs leading to death

Summaries will be presented by MedDRA System Organ Class (SOC) and Preferred Term (PT) using frequency counts and percentages (i.e., number and percentage of subjects with an event). When summarizing the number and percentage of subjects with an event, subjects with multiple

occurrences of the same AE or a continuing AE will be counted once. Only the maximum severity level will be presented in the severity summaries, and the strongest relationship level will be presented in the relationship summaries.

In addition, a listing containing individual subject AE data for TEAEs leading to treatment discontinuation, SAEs, and deaths will be provided separately. All AEs, including pretreatment AEs, will be presented in an individual subject data listing.

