#### **12.3.4.2 Clinical Laboratory Assessments**

For the treatment-emergent laboratory measurements, the raw values and change from baseline values of the continuous laboratory parameters will be summarized in SI units by treatment group at each scheduled time point. In addition, mean value at each visit will be plotted by treatment groups for each of the liver function parameters.

The number and percentage of subjects with at least 1 categorical change during the TE Period will be summarized by treatment group. The categorical (post-baseline) shift from baseline will also be summarized for selected laboratory parameters. The categorical criteria and the parameter selection criteria will be provided in the SAP. In addition, a listing containing individual subject laboratory assessment values outside the reference ranges will be provided. This listing will include data from scheduled and unscheduled time points.

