#### **12.3.4.6 Other Safety Analysis**

The above safety analysis will be performed by treatment arm from baseline to Week 48, as well as from baseline to Week 96. In addition, a similar safety analysis like the above will be performed separately for placebo→LUM/IVA arm from Week 48 (before to LUM/IVA dose) through the end of the Safety Follow-up after Week 96, where predose measurement at Week 48 will be used as the baseline value.

Details of the analysis will be provided in the SAP.

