3 INTRODUCTION

This statistical analysis plan (SAP) for the Part 1 (interim) and final analysis is based on the most recent approved clinical study protocol (CSP), electronic case report form (eCRF), and eCRF completion guidelines.

This SAP (Methods) documents the planned statistical analyses of efficacy and safety endpoints for the Part 1 analysis and the final analysis (FA), which have been pre-defined in the VX16-809-121 study protocol. It also documents analyses for [REDACTED] safety variables not specified in the protocol, which will provide supportive information for the scientific understanding of the drug entity.

The Vertex Biometrics Department will perform the statistical analysis of the efficacy and safety data; SAS (Version 9.4 or higher) will be used to generate all statistical outputs (tables, figures, listings, and datasets). The SAP will be finalized and approved prior to the Part 1 analysis data-cut and treatment unblinding for the Part 1 analysis. Any revisions to the approved SAP will be documented and approved in an amendment to the SAP prior to the clinical database lock for the final analysis. Any changes made to the SAP (Methods) after the clinical database lock has occurred will be documented in the clinical study report for this study.

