7 ANALYSIS SETS

The following analysis sets are defined: All Subjects Set, Full Analysis Set, [REDACTED] and Safety Set.

A summary of analysis sets is presented in Table 7-1.

Table 7-1 Summary of Analysis Sets

Analysis Set	Target Analyses	Treatment Group/Sequence
All Subject Set ^a	Individual subject listing and disposition summary for Part 1 analysis	
 LUM/IVA PBO
Full Analysis Set (FAS) ^a	Efficacy and baseline demographic for Part 1 analysis	
 LUM/IVA PBO
	By-visit efficacy summary for FA	
 LUM/IVA→LUM/IVA PBO→LUM/IVA

Safety Set ^b	Safety for Part 1 analysis	
 • LUM/IVA • PBO
	Part 2 safety analysis, individual subject listing, and disposition summary for FA	OR 
 • Overall LUM/IVA • LUM/IVA→LUM/IVA • PBO→LUM/IVA

^a Treatment label is based on the treatment the subject was randomly assigned to in the study Part 1 or the corresponding treatment sequence from Part 1 to Part 2.

^b Treatment label is based on the treatment that the subject received in the study Part 1 or its corresponding treatment sequence from Part 1 to Part 2.

[figure not shown]
FA: final analysis; IVA: ivacaftor; LUM: lumacaftor; PBO: placebo

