8.4 Part 2 Safety Period

The **Part 2 Safety Period** will include the time from the first dose of study drug of Part 2 until 14 days after the last dose of LUM/IVA or the completion of study participation, whichever occurs first.

Completion of study participation is defined as:

- For subjects who complete the study, the latest of the ETT Visit or Safety Follow-up Visit (if required).
- For subjects who prematurely discontinue study drug treatment during the study but do not withdraw consent (and assent, as applicable): the latest of ETT or Safety Follow-up Visit (if required).
- For subjects who withdraw consent or assent: date of withdrawal of consent or assent, whichever is earlier.

The Part 2 Safety Period will be used for analysis of safety data in the FA.

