9 STATISTICAL ANALYSIS

9.1 General Considerations

As summarized in Table 7-1, the 2 treatment groups in Part 1 are

- LUM/IVA
- Placebo (PBO)

and the 2 treatment sequences from Part 1 to Part 2 are as follows:

- LUM/IVA → LUM/IVA
- PBO → LUM/IVA

Continuous variables will be summarized using the following descriptive summary statistics: the number of subjects (n), mean, SD, median, minimum value (min), and maximum value (max).

Categorical variables will be summarized using counts and percentages.

Unless otherwise specified,

- the **Study Baseline** value is defined as the most recent non-missing measurement (scheduled or unscheduled) collected before the first dose of study drug (including the matched placebo). The study baseline will be used to calculate the absolute and relative change from baseline for efficacy analyses, unless otherwise specified.
- the **LUM/IVA Baseline** value is defined as the most recent non-missing measurement (scheduled or unscheduled) collected before the first dose of study drug of Part 1 if the subject actually received at least one dose of LUM/IVA in Part 1, or before the first dose of study drug of Part 2 if the subject did not actually receive at least one dose of LUM/IVA in Part 1. The LUM/IVA baseline will be used to calculate the change from baseline in safety analysis in the FA, unless otherwise specified.

Absolute change from baseline will be calculated as post-baseline value – baseline value.

Relative change from baseline will be calculated as (post-baseline value – baseline value)/baseline value.

Unscheduled visits: Unscheduled visit measurements will be included in analysis as follows:

- 1) In scheduled visit windows per specified visit windowing rules
- 2) In the derivation of baseline and last on-treatment measurements
- 3) In the derivation of maximum and minimum values, and maximum and minimum change from baseline values during analysis period for safety analyses
- 4) In individual subject data listings as appropriate

Visit windowing rules: The analysis visit windows for protocol-defined visits are provided in [Appendix A](#).

Incomplete/missing data will not be imputed, unless specified otherwise.

Outliers: No formal statistical analyses will be performed to detect or remedy the presence of statistical outliers, unless specified otherwise.

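### The SAP pools the Part 2 TEAE and laboratory-threshold tables over all LUM/IVA children, although the protocol plans a separate safety analysis of the placebo→LUM/IVA arm

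*SAP*

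**What the plan says.** Protocol 12.3.4.6 sets out three safety presentations: by arm from baseline to Week 48, by arm from baseline to Week 96, and a third in which "a similar safety analysis like the above will be performed separately for placebo→LUM/IVA arm from Week 48". The third runs through the Safety Follow-up after Week 96, takes the Week 48 predose value as baseline, and leaves details to the SAP.

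The analysis to be repeated includes:
- the TEAE tables of Protocol 12.3.4.1 ("AE summary tables will be presented for TEAEs only, overall and by treatment group, and will include the following");
- the laboratory counts of Protocol 12.3.4.2 ("The number and percentage of subjects with at least 1 categorical change during the TE Period will be summarized by treatment group").

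SAP 3 states that it documents the planned efficacy and safety analyses "which have been pre-defined in the VX16-809-121 study protocol". For the final analysis, SAP 9.3.3 has two presentation rules. Adverse-event and threshold analyses, unless other text overrides, "will be summarized for the Part 2 Safety Period and presented for overall LUM/IVA treatment group". Changes from LUM/IVA baseline in laboratory values and vital signs are shown by treatment sequence. SAP 9.3.3.1 (adverse events) and 9.3.3.2 (laboratory and vital signs) add no sequence split for TEAE or threshold tables.

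SAP Table 7-1 has a Safety Set row for "Part 2 safety analysis, individual subject listing, and disposition summary for FA". Beside it stand the overall LUM/IVA group and both sequences, with an OR whose scope is unclear in the extracted text.

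**The concern.** For the placebo children, Part 2 is the first exposure to active drug. The others in the pooled column have already had 48 weeks of it. A single percentage over both groups cannot show whether events or threshold crossings are more frequent in the children who are starting.

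The protocol asks for a summary that would show this for the starters. The SAP, followed as written, does not produce it for TEAEs or laboratory thresholds and does not say that it was dropped. A reader of the study report would find a protocol-specified table missing without explanation.

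**Working it through.** The point rests on the text, and the plan states no figure to reproduce. The passages compare as follows.

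| Item | Protocol 12.3.4.6 | SAP, final analysis |
|---|---|---|
| Period for starters | Week 48 to Safety Follow-up | Part 2 Safety Period, from the first Part 2 dose (8.4): compatible |
| Baseline for starters | Week 48 predose | Last value "before the first dose of study drug of Part 2 if the subject did not actually receive at least one dose of LUM/IVA" during Part 1 (9.1): agrees |
| Laboratory and vital-sign changes | Separately for starters | By sequence (9.3.3, 9.3.3.2): agrees |
| TEAE tables | Separately for starters | Overall LUM/IVA group (9.3.3): differs |
| Laboratory threshold or categorical counts | Separately for starters | Overall LUM/IVA group (9.3.3): differs |

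The last two rows are the discrepancy.

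**Share of starters in the pooled column.** The planned sizes are 33 LUM/IVA and 17 placebo (SAP 6.2).
- All enter Part 2: 17/(33 + 17) = 17/50 = 34%.
- Assumed 10% loss in each arm before Part 2: 33 × 0.9 ≈ 30 and 17 × 0.9 ≈ 15, so 15/45 = 33%.

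**What a pooled count can hide.** The counts are illustrative, because the documents give no event rates. If 4 of 50 children have an event (8.0%), the table cannot distinguish these splits:

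| Starters | Continuers |
|---|---|
| 4/17 = 23.5% | 0/33 = 0% |
| 3/17 = 17.6% | 1/33 = 3.0% |
| 2/17 = 11.8% | 2/33 = 6.1% |
| 1/17 = 5.9% | 3/33 = 9.1% |
| 0/17 = 0% | 4/33 = 12.1% |

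The range of compatible starter rates for other pooled counts:
- 2/50 (4.0%): 0% to 2/17 = 11.8%.
- 6/50 (12.0%): 0% to 6/17 = 35.3%.
- 4/45 (8.9%) with 30 continuers and 15 starters: 0% to 4/15 = 26.7%.

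**Dilution under assumed rates.** Pooled rate = (33 × p_continuers + 17 × p_starters)/50.
- 5% and 20%: (1.65 + 3.40)/50 = 10.1%.
- 10% and 30%: (3.30 + 5.10)/50 = 16.8%.
- Equal rates: the pooled rate is the common rate and nothing is hidden.

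**Precision of a starter column.** For 4/17 the exact (Clopper-Pearson) 95% interval is 6.8% to 49.9%. The column would describe the starters and could not support a firm comparison.

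**The case against.** The strongest reply is that the SAP does not firmly exclude the starters. The pooled rule in 9.3.3 yields to other text, Table 7-1 names the placebo→LUM/IVA sequence for Part 2 safety, and 9.3.3 says the Part 1 analyses, which are by treatment group, are carried over in similar form. But 9.3.3 is the more specific text. It assigns the overall group to adverse events and thresholds, and the sequences to laboratory and vital-sign changes. Table 7-1 fits that division, and no readable text overrides it.

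A second reply is that parts of the SAP are not visible. Section 8.3 is blanked, Appendix C mentions a cumulative safety period that the readable text does not define, and a figure is missing after the threshold paragraph in 9.3.3.2. The point is therefore limited to readable text, and nothing blanked is counted as an omission. SAP 8.4 does state: "The Part 2 Safety Period will be used for analysis of safety data in the FA".

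A third reply is that the protocol gives only a summary and leaves details to the SAP. That allows choice of layout, but a pooled column is not a separate analysis.

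The last reply, that little is lost, largely stands. The study is exploratory, safety is descriptive, no primary or secondary endpoint is touched, and Part 1 compares initiation with placebo. TEAEs and laboratory values are listed by subject, so starter counts could be rebuilt. However, the protocol plans listings in addition to summaries. Part 1 also shows initiation in other children, and Protocol Table 9-2 lists the regimen for children aged 6 or over under Part 2 only.

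**Conclusion.** The discrepancy is real. Protocol 12.3.4.6 specifies a separate safety analysis of the placebo→LUM/IVA arm from Week 48. The readable SAP delivers it for laboratory and vital-sign changes but not for TEAE or laboratory-threshold tables, and records no departure.

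The affected children are about one third of the pooled column, assuming that all planned subjects enter Part 2 or that 10% of each arm drop out first. How much the pooling would conceal depends on event rates that the documents do not give. This should be corrected, but it does not threaten the trial's main conclusions.

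**What to change.** In SAP 9.3.3, 9.3.3.1 and 9.3.3.2, present the Part 2 TEAE and laboratory-threshold tables by treatment sequence (LUM/IVA→LUM/IVA and PBO→LUM/IVA) as well as overall. The protocol strictly requires only the PBO→LUM/IVA column; the continuing column makes the comparison readable. State in Table 7-1 which tables use which grouping. If the pooled presentation is intended, record it, with the reason, as a departure from Protocol 12.3.4.6.

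Optionally, and beyond what the protocol asks, apply the same split to the special-interest-event tables that the SAP adds, and state the dose from which Part 2 time to onset is counted.

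The cost is two extra columns with small, imprecise denominators in tables already planned. The sequences are defined in SAP 9.1 and already used for Part 2 disposition, protocol deviations, and laboratory and vital-sign changes. The Part 2 Safety Period already begins at the starters' first active dose, so no new analysis period is needed. SAP 3 allows amendment before the database lock for the final analysis.
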